#### **1.4 Preliminary Data**

There is no preliminary data.

#### **1.5 Sample Size Justification**

The goal of this study was to find a change in the pain score that would be clinically relevant. A 2 point reduction in the 10 point VAS was deemed as clinically significant. To detect a difference of at least 2 points with at least 90% power, two sided alpha 0.05, and a standard deviation of 3, this study required at least 48 women per arm.

#### **1.6 Study Variables**

##### **A. Independent Variables, Interventions, or Predictor Variables**

The intervention being tested is music. Patients will receive either routine pain control measures only (control group) or routine pain control measures and music (treatment group). Routine pain control will include instructions to take ibuprofen 600 mg 30 minutes prior to the procedure. These instructions will be given to all participants. It will be noted whether patients actually take ibuprofen or not by the study staff. Patients randomized to receive music in addition to routine pain control measures, will listen to preselected classical music played on the PI phone.

##### **B. Dependent Variables or Outcome Measures**

Pain is the primary outcome measure. Pain will be measured on the VAS. Anxiety is the secondary outcome measure. Anxiety will be measured on the STAI

#### **1.7 Drugs/Devices/Biologics**

This study will use two different IUDs which are both FDA approved for this indication: Mirena® (levonorgestrel-releasing intrauterine system 52 mg) or Paragard® (intrauterine copper contraceptive). These will be inserted into the uterus by a physician at bedside.

##### **A. Drug/Device Accountability and Storage Methods**

For both RWJ and RMG, the IUDs are stored and secured in the Ob/Gyn department in CAB building. At both locations, nursing staff is responsible for preparation of the IUD. At both locations, an Ob/Gyn Physician will be inserting the IUD.

#### **1.8 Specimen Collection**

##### **A. Primary Specimen Collection**

No specimens will be collected in this study.

- **Types of Specimens:** N/A
- **Annotation:** N/A
- **Transport:** N/A
- **Processing:** N/A
- **Storage:** N/A
- **Disposition:** N/A

**B. Secondary Specimen Collection**

No specimens will be collected in this study.

- **Types of Specimens:** N/A
- **Annotation:** N/A
- **Transport:** N/A
- **Storage:** N/A
- **Disposition:** N/A

**1.9 Data Collection**

**A. Primary Data Collection**

- **Location:** At both RWJ and RMG, data collection will take place within two main areas: the waiting room and the patient exam room.
- **Process of Data Collection:** In the waiting room, patients will complete the demographic survey. They will also complete, the VAS and STAI for their baseline pain and anxiety scores, respectively. If the patient wishes to complete any of these instruments in private, she will be led into an unoccupied patient exam room. In the exam room, the providers will complete the provider survey regarding the patient. The providers will also record vital signs, BMI, and other pertinent medical information. While in the exam room, at several points through the insertion the VAS and STAI will be administered.
- **Timing and Frequency:** The patient survey will be completed once by the patient while she is in the waiting room. The provider survey will be completed once by the provider while the patient is in the exam room. The VAS will be completed by the patient at several points: immediately prior to the procedure, point of speculum insertion, point of tenaculum placement, point of IUD insertion, and 5 minutes post-procedure. The STAI will be completed immediately prior to the procedure and 5 minutes post-procedure.
- **Procedures for Audio/Visual Recording:** There will be no audio or video recordings of the patients.
- **Study Instruments:** The patient survey will include demographic information including: age, ethnicity, preferred language, marital status, education level, history of smoking, history of alcohol use, current medications, allergies, date of last menstrual period, menstrual history, exercise habits, current pain level, current anxiety level, history of depression, music interests, prior medical procedures, prior medical complications, pregnancy history, delivery history, miscarriage history, previous pain management techniques, and preferred method of music listening. The provider survey includes heart rate, blood pressure, respiration rate, body mass index (BMI), type of IUD inserted, medical complications, prior contraceptive use, gravidity, parity. The VAS is a well known and accepted instrument for quantifying pain. It has been used previously to report pain during IUD insertion (Mody 2018). The STAI is also a well known and accepted instrument for quantifying anxiety. It, too, has also been used previously to report anxiety in several different circumstances (Kendall 1976).
- **Ethnographic Studies, Interviews, Or Observation:** N/A
- **Subject Identifiers:** N/A

**B. Secondary Data Collection**

No data of this type will be collected.

- **Type of Records:** N/A
- **Location:** N/A
- **Inclusion/Exclusion:** N/A
- **Data Abstraction Form(s):** N/A

**1.10 Timetable/Schedule of Events**

Once we start recruiting patients after the IRB is approved, we expect it will take one to two years to achieve our prespecified sample size. At this point, the study will be concluded and we will analyze the data.

### **2.2 Research Staff Training**

Thus far, in designing this project, the research staff has been holding monthly meetings to discuss the research protocol. These meetings also serve to identify upcoming goals, concerns, and questions. These meetings will continue and will function to disseminate information regarding the research procedures and the duties and functions of each study staff member. [name] will be present during all IUD insertions at RMG and RWJ and will serve to oversee and standardize all recruitment, consent, and date collections activities.

### **2.3 Resources Available**

The majority of the resources required for any IUD insertion are those that are part of routine care. The only additional resources required are those related to the study intervention. In order to play music, this study requires a headset, which will be plugged into [name] phone, which is a HIPAA compliant phone provided by RWJMS. This headset will be completely funded by the study investigators. The study intervention is anticipated to cause no medical or psychological harm to the patient.

### **2.4 Research Sites**

Gynecology clinic inside Robert Wood Johnson University Hospital (RWJ) and the offices of Rutgers Medical Group Obstetrics and Gynecology (RMG). There are no international research sites.

## **3.0 Multi-Center Research**

## **4.0 Subject Considerations**

### **4.1 Subject Selection and Enrollment Considerations**

#### **A. Method to Identify Potential Subjects**

All women with an appointment for IUD placement at RMG or RWJ who are able to read and write in English will be considered eligible for the study.

**B. Recruitment Details**

All eligible patients will be approached by a member of the study staff while they are sitting in the waiting room prior to their IUD insertion appointment. Each individual patient will be taken to an unoccupied patient examination room where, after briefly describing the study, the study staff will ask each eligible patient if she is willing to participate. No additional materials will be used to accomplish the recruitment efforts.

**C. Subject Screening**

The study staff member will review inclusion and exclusion criteria for all eligible women prior to consenting them to participate in an otherwise unoccupied patient examination room.

**▪ Inclusion Criteria**

The inclusion criteria for this study are (1) Women who have an appointment for IUD insertion at either RWJ or RMG **AND**(2) Women who are able to read and write in English or Spanish **AND** (3) Age equal to or greater than 18 years.

**▪ Exclusion Criteria**

Exclusion criteria included contraindications to IUD placement: Active pelvic infection, pregnancy, known distortion of uterine cavity, Wilson's disease (Paragard® only), breast cancer (Mirena® only)

**4.2 Secondary Subjects**

There are no secondary subjects.

**4.3 Number of Subjects**

**A. Total Number of Subjects**

A total of 48 women per arm, or 96 total subjects are necessary to complete this project. We expect that approximately 200 women will need to be screened to successfully enroll 96 subjects.

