**C. Study Duration**  
Each subject will participate only once during their actual outpatient appointment for IUD insertion. The overall duration of this study will be until the prespecified sample size determined based on power calculation is reached. This is estimated to take approximately 1 to 2 years.

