## 6.0 Data Management Plan

### 6.1 Data Analysis

Power analysis was completed to determine the sample size to be collected for each arm.

The results will be analyzed using t-tests and its nonparametric equivalent to determine if there is a difference in pain and anxiety scores between the two arms.

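### The claim of at least 90% power rests on 48 women per arm with no allowance for missing pain scores, and is about 90% at most for the planned tests at the stated SD

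*Combined protocol and SAP*

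**What the plan says.** Section 1.5 gives the inputs: "To detect a difference of at least 2 points" on the 10-point VAS, "with at least 90% power", "two sided alpha 0.05" and "a standard deviation of 3". From these it concludes that "this study required at least 48 women per arm".

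Section 4.3 A carries the figure over as the enrolment total: "A total of 48 women per arm, or 96 total subjects are necessary to complete this project". It adds that about 200 women will be screened to enrol 96. Section 1.3 C runs the study "until the prespecified sample size determined based on power calculation is reached", and section 1.10 closes it at that point.

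Section 1.3 A treats a woman as enrolled once she is eligible and willing to be randomized. Randomization follows the baseline forms, so it comes before any pain score taken during the procedure.

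Section 6.1 sets the analysis: "The results will be analyzed using t-tests and its nonparametric equivalent". No section gives a rate of loss after randomization, a replacement rule or a rule for missing scores.

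**The concern.** A power formula counts women whose scores enter the analysis. Sections 4.3 A and 1.3 C count women enrolled. The plan uses one number for both and does not say what happens if they differ. The 200-to-96 ratio does not close the gap, because it covers screening and refusal and ends at enrolment.

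The wording of the power claim is the second part. It is given as a floor, while the 48 comes from an approximation that is slightly more favourable than either test named in section 6.1.

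What is at stake is how a null result would be read. Section 1.2 cites a meta-analysis in colposcopy that found no benefit of music and a trial in abortion that found more pain with it, so a null result here is plausible. Readers would then take the chance of having missed a true 2-point difference to be at most 10%.

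**Working it through.** **Inputs.** From section 1.5: difference 2, SD 3, two-sided alpha 0.05, power 90%. From section 1.3 A: 1:1 allocation. From section 6.1: t-test and its nonparametric equivalent, taken here as the Wilcoxon rank-sum test. The loss rates below are assumptions, since the documents give none.

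**Step 1: the plan's own figure.** Normal approximation, n per arm = 2 × (SD × (z₀.₉₇₅ + z₀.₉₀) / difference)² = 2 × (3 × (1.960 + 1.2816) / 2)² = 47.28, rounded up to 48. The plan's figure is reproduced exactly, with no inflation for loss.

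**Step 2: room left under that formula.** Power = Φ(2 / (3 × √(1/n₁ + 1/n₂)) − 1.960).

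| Scored per arm | Power |
|---|---|
| 48 + 48 | Φ(3.266 − 1.960) = 90.4% |
| 48 + 47 | Φ(3.249 − 1.960) = 90.1% |
| 47 + 47 | Φ(3.232 − 1.960) = 89.8% |

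Rounding up therefore absorbs one missing woman. Power drops below 90% at the second.

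**Step 3: the planned t-test.** Power comes from the noncentral t distribution with n₁ + n₂ − 2 degrees of freedom and noncentrality 2 / (3 × √(1/n₁ + 1/n₂)). At 48 per arm there are 94 degrees of freedom, the critical value is 1.986, the noncentrality is 3.266, and power is 89.84%. At 49 per arm it is 90.43%, so 49 is the first size at or above 90%.

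**Step 4: the rank test.** Under normality its relative efficiency to the t-test is 3/π = 0.955. Power at 48 per arm is then roughly that of a t-test with 48 × 0.955 = 45.8 per arm, which is 88.4%.

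**Step 5: fewer women scored.** Equal numbers per arm, difference 2, SD 3:

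| Scored per arm | Unscored of 96 | t-test | Rank test (normality) |
|---|---|---|---|
| 48 | 0 | 89.8% | 88.4% |
| 46 | 4 (4.2%, near an assumed 5%) | 88.6% | 87.1% |
| 43 | 10 (10.4%, near an assumed 10%) | 86.3% | 84.7% |

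The corresponding t-test chances of missing a true 2-point difference are 100 − 89.8 = 10.2%, 100 − 88.6 = 11.4% and 100 − 86.3 = 13.7%.

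**The case against.** **There is no arithmetic error.** This stands. The inputs give 48, the normal approximation is an ordinary planning formula, and the t-test shortfall with complete data is 0.16 percentage points, or one woman per arm. Section 1.5 also words its 48 as a minimum. But sections 4.3 A and 1.3 C then treat that minimum as the stopping point.

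**Loss is likely to be low.** This is a fair point. Participation is one visit (section 1.3 C), a staff member is in the room throughout (section 1.3 A), and the last score is due 5 minutes after the procedure (section 1.9 A). The documents still give no rate. The score at IUD insertion exists only if the procedure reaches that step. Sections 1.3 D and 1.6 B do not name the primary time point, so it is not settled which missing score would remove a woman from the analysis.

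**The SD matters more.** This also stands. Section 1.4 reports no preliminary data. With SD 2.8, t-test power is 93.4% at 48 per arm and 90.6% at 43; with SD 3.1 it is 87.9% at 48. The figures above hold only at the plan's own SD.

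**The rank-test figure assumes normality**, where that test is least needed. With skewed or heavy-tailed scores it may do as well as the t-test or better. The 88.4% therefore needs its condition stated.

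**Stronger readings that a reader might infer.** One is that the first missing score breaks the 90% claim. It does not: the plan's formula still gives 90.1% with one woman missing, and the t-test is already just under 90% with none missing. Another is that the false-negative risk will be 12 to 15%. That needs roughly 6 to 15% of women unscored, which nothing in the documents supports.

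**Conclusion.** The point holds in a narrow form. The number to enrol equals the uninflated number to analyse, no loss allowance or replacement rule exists, and power is stated as a floor that neither planned test strictly meets at the plan's own inputs: 89.8% for the t-test, and about 88.4% for the rank test under normality, with all 96 scored. Missing scores lower both figures. The t-test loses about 1.3 points at 46 scored per arm (89.84 − 88.55) and 3.5 points at 43 (89.84 − 86.34).

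These results rest on difference 2, SD 3, equal arms and scores missing for reasons unrelated to pain. The loss rates are illustrations. This is a minor matter of how power is reported. It does not show that the trial is too small to be useful.

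**What to change.** Keep enrolment at 96 and correct the statement of power.

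- **Section 1.5:** replace the at-least-90% claim with wording such as: *approximately 90% power (t-test 89.8%; rank test about 88% under normality) if all 96 randomized women have a pain score, and lower if scores are missing (for illustration, t-test 88.6% with 46 scored per arm and 86.3% with 43).*
- **Section 4.3 A:** state that 96 is the number of women randomized.

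Do not define the 48 per arm as women with a score while keeping enrolment at 96. Under that definition any loss would require replacement or a larger enrolment, and the two statements would conflict.

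The cost is one sentence in each section and a slightly less favourable power figure. No additional women, procedures or time are needed.

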**B. Total Number of Subjects If Multicenter Study**

N/A

**C. Feasibility**

In an average month, 20 women are seen for IUD insertion between both sites (RMG and RWJ). As the study intervention (music) confers no additional risk to routine management during IUD insertion, we anticipate that at least half of these women will consent to participate in the study. If approximately 10 women are enrolled in the study monthly, then we believe it is feasible to complete this study in little over a year.

**4.4 Consent Procedures**

**A. Consent Process**

**▪ Location of Consent Process**

The consent process will take place in private in an otherwise unoccupied patient examination room of either RMG or RWJ prior to the patient's appointment.

**▪ Ongoing Consent**

Ongoing consent is not required as the patient will only participate in the study for the duration of their appointment.

**▪ Individual Roles for Researchers Involved in Consent**

[name], [name], and [name] will all be responsible for approaching/recruiting patients, discussing the study, determining inclusion and exclusion criteria, and subsequently consenting patients desiring to participate.

- **Consent Discussion Duration**  
The consent discussion is anticipated to take five to ten minutes with additional time devoted as necessary to answer any and all questions from a potential subject.
- **Coercion or Undue Influence**  
Prior to the conclusion of the consent process, all potential subjects will be reminded that participation in the study is purely voluntary and their refusal to participate will not impact their access to or the quality of care.
- **Subject Understanding**  
The teachback method will be utilized so that patients will restate everything explained to them in their own words to ensure that they comprehend the key study elements. There will be several opportunities for the patients to ask questions throughout the consent discussion.

**B. Waiver or Alteration of Consent Process**

- **Waiver or Alteration Details**  
N/A
- **Destruction of Identifiers**  
N/A
- **Use of Deception/Concealment**  
This research plan does not involve deception or concealment.
  - a. **Minimal Risk Justification**  
N/A
  - b. **Alternatives**  
N/A
  - c. **Subject Debriefing**  
N/A

**C. Documentation of Consent**

- **Documenting Consent**  
Both the study staff member obtaining consent and the patient electing to participate in the study will sign and date the consent document. The participants will be provided with a copy of the consent document to retain for their records.
- **Waiver of Documentation Of Consent (i.e., will not obtain subject's signature)**  
We will be obtaining signatures from all participants.

**4.5 Special Consent/Populations**

**A. Minors-Subjects Who Are Not Yet Adults**

- **Parental Permission**  
N/A
- **Non-Parental Permission**  
Non-parental permission will not be obtained.
- **Assent Process**  
N/A
- **Documentation of Assent**  
N/A
- **Reaching Age of Majority During Study**  
N/A

**B. Wards of the State**

- N/A
- **Research Outside of NJ Involving Minors**  
N/A

**C. Non-English-Speaking Subjects**

Patients able to read and write in Spanish will be included in this study.

▪ **Process for Non-English-Speaking Subjects**

A study staff member certified in Spanish interpretation will obtain consent from all patients who are able to read and write in only Spanish and not English. A Spanish consent form will be used for these patients.

▪ **Short Form Consent for Non-English Speakers**

N/A

**D. Adults Unable to Consent / Decisionally Impaired Adults**

Decisionally Impaired adults will not be recruited to participate in this study.

▪ **NJ Law-Assessment of Regaining the Capacity to Consent**

N/A

▪ **Capacity to Consent**

N/A

    a. **NJ Law-Selecting A Witness**

N/A

    b. **Removing a Subject**

N/A

**4.6 Economic Burden and/or Compensation for Subjects**

**A. Expenses**

There will be no monetary cost to the patient for participating in the research.

**B. Compensation/Incentives**

There will be no monetary compensation or incentives provided to the patient for participating in the research.

**C. Compensation Documentation**

N/A

**4.7 Risks of Harm/Potential for Benefits to Subjects**

**A. Description of Risks of Harm to Subjects**

▪ **Reasonably Foreseeable Risks of Harm**

Patients who participate in the study will almost certainly have a longer visit. Between the consent process and the patient survey that participants will need to complete, it is estimated that approximately 20 minutes will be added on to the patient's appointment. Other than this loss of time, there are no other inconveniences or harms that are foreseeable. The study intervention of music is not associated with any known harm.

▪ **Risk of Harm from an Intervention on a Subject with an Existing Condition**  
N/A.

▪ **Other Foreseeable Risks of Harm**

There are minimal risks associated with possible loss of confidentiality. However, since patients will be signing the consent form with their names, a potential risk of breach of confidentiality does exist.

▪ **Observation and Sensitive Information**  
N/A.

**B. Procedures which Risk Harm to Embryo, Fetus, and/or Pregnant Subjects**

Pregnancy is an exclusion criteria.

**C. Risks of Harm to Non-Subjects**

Non-subjects will not be involved in this research in any capacity.

**D. Assessment of Social Behavior Considerations**

N/A

**E. Minimizing Risks of Harm**

The only harm of this study is the inconvenience of dedicating additional time to the patient visit. This will be minimized as much as possible by including the consent process during the time the patient is waiting prior to her appointment. All data sheets will be kept locked in the [name] office. All electronic data will be stored in an encrypted hospital computer.

- Certificate of Confidentiality**

N/A.

- Provisions to Protect the Privacy Interests of Subjects**

The only people the participants will be providing information regarding the research to will be the study staff members and the physician and nurse assigned to her for the visit. This will serve to limit the number of people the participant interacts with or provides personal information to about the research. In subsequent appointments, their participation in the research will not be referenced unless the conversation is initiated by the former participant.

**F. Potential Benefits to Subjects**

Music has been previously shown to reduce pain and anxiety related to procedures as well as related to chronic diagnoses. This study seeks to determine if music has this effect during IUD insertion, as well. Patients who take part in this research and are randomized to the intervention group are anticipated to experience a decrease in pain and anxiety during their IUD insertion. We anticipate that this effect will last for the duration of the procedure and that it will reduce pain and anxiety by approximately 25%.

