assessing the effect of music therapy showed no difference in anxiety levels (n=763, p=0.4) or pain (n=649) during (p=0.31) and after (p=0.33) colposcopy. (Abdelhakim, 2019). Similarly, a randomized control trial of 101 women randomized to undergo abortion with routine pain control measures only (ibuprofen and paracervical block) or with the addition of intraoperative music via headphones showed that intraoperative music, in fact, increased reported pain (p=0.045) (Guerrero, 2012). Due to these conflicting reports, our study aims to explore music therapy as a pain management strategy during LARC insertion specifically.

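### Does the 25% benefit anticipated in Section 4.7 undermine the 90% power claimed for a 2-point difference?

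*Combined protocol and SAP*

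**What the plan says.** Section 1.5 sets the target: "A 2 point reduction in the 10 point VAS was deemed as clinically significant". The sample size follows from it: "To detect a difference of at least 2 points with at least 90% power, two sided alpha 0.05, and a standard deviation of 3", giving 48 women per arm. Section 4.3 repeats this as 96 in total. Section 1.4 states that no preliminary data exist, and no control-arm mean pain score appears anywhere.

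Section 4.7 F, on potential benefits, anticipates less pain and anxiety in the music arm, and that "it will reduce pain and anxiety by approximately 25" per cent. It does not say what the percentage is taken of. Section 4.7 A states: "The study intervention of music is not associated with any known harm". Section 4.7 E names added visit time as the only harm.

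Section 1.2 cites a favourable meta-analysis across many kinds of pain, a colposcopy meta-analysis with no difference in pain or anxiety, and a randomized abortion trial of 101 women in which "intraoperative music, in fact, increased reported pain (p=0.045"). It describes these reports as conflicting and gives that as the reason for the study.

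Section 6.1 plans t-tests and a nonparametric equivalent on pain and anxiety scores. It does not mention an estimate or a confidence interval.

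**The concern.** The protocol carries two effect sizes and never relates them. A reader who takes 25% as the investigators' real expectation, and as a fraction of control-arm pain, finds that it reaches 2 points only if control patients average 8 out of 10. At any lower mean the anticipated benefit is smaller than the protocol's own threshold for relevance, and power to detect it is below the 90% quoted. A non-significant result could then be misread as showing that music does not help, especially since Section 6.1 names only tests.

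The risk and benefit text raises a separate issue. It presents only the favourable evidence and denies any known harm, although Section 1.2 cites a trial in which music made pain worse. Pain is this trial's primary outcome, and Section 2.3 shows that the music here is also delivered through a headset.

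**Working it through.** **Inputs.** From Section 1.5: difference 2 points, SD 3, two-sided alpha 0.05, power 90%, 48 per arm. From Section 1.3 A: 1:1 allocation. From Section 4.7 F: a reduction of about 25%. The control-arm mean is not in the documents, so the values below are assumptions.

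**1. The plan's own figure.** By the normal approximation,

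n per arm = 2 × [SD × (z₀.₉₇₅ + z₀.₉₀) / difference]² = 2 × [3 × (1.960 + 1.282) / 2]² = 47.3, rounded up to 48.

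Power at 48 per arm is 90.4% by this approximation. The noncentral t gives n = 48.3 and 89.8% power at 48. The stated sample size reproduces.

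**2. Where 25% equals 2 points.** If the 25% is of the control mean, the mean must be 2 / 0.25 = 8.0. By the normal approximation, 48 per arm has exactly 90% power for 1.985 points, which puts the break-even mean at 1.985 / 0.25 = 7.94.

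**3. Power for a 25% reduction**, 48 per arm, SD 3, noncentral t:

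| Assumed control mean | 25% of it (points) | Power |
|---|---|---|
| 4 | 1.00 | 37% |
| 5 | 1.25 | 52% |
| 6 | 1.50 | 68% |
| 7 | 1.75 | 81% |
| 8 | 2.00 | 90% |
| 9 | 2.25 | 95% |
| 10 | 2.50 | 98% |

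**4. Sensitivity to the reading and to the SD.** If 25% means a quarter of the 10-point scale, the effect is 0.25 × 10 = 2.5 points and power is 98%. If it is of the control mean but the SD is 2.5, power by the normal approximation is 69%, 84%, 93% and 97.5% at means of 5, 6, 7 and 8. The shortfall therefore depends on three things the documents do not settle: the base of the percentage, the control mean, and the SD actually observed.

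**5. Reading a null result.** With SD 3 and 48 per arm, the standard error of the difference is 3 × √(2/48) = 0.612. The 95% half-width, and the smallest significant observed difference, is 1.9855 × 0.612 = 1.22 points. A non-significant result with an observed benefit below 2 − 1.22 = 0.78 points would exclude a 2-point benefit. One between 0.78 and 1.22 would not. The interval that shows this uses the same standard error as the planned t-test.

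**6. The adverse trial and the design.** The test in Section 1.5 is two-sided. By symmetry it has the same power for 2 points more pain with music as for 2 points less. The possibility raised by the cited trial is already covered, and that trial has no bearing on the power figure.

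**The case for a change.** The best case for acting is that the 25% is the protocol's only statement of what the investigators expect, and its ordinary reading is relative to control. On that reading, at every control mean below 8 and whatever the SD, the anticipated benefit is smaller than the 2 points called clinically significant. At means of 6 or less the power shortfall remains even with an SD of 2.5. The remedy would cost only a few sentences: define or delete the 25%, and commit to a confidence interval read against 2 points. The contradiction over harm needs no assumption at all.

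Much of this stands as description. The arithmetic is right, the two effect sizes are unreconciled, and the denial of known harm is hard to square with Section 1.2. It does not show a wrong figure or a weak design. Powering for a minimum relevant difference is standard practice, and that difference need not equal the expected one. The protocol nowhere claims 90% power for a 25% reduction. A power table by control mean would put values into Section 1.5 that the documents give no basis for. The 25% could be deleted without touching the sample size or the analysis, which shows that nothing rests on it. A confidence interval alongside a t-test is what any analyst would report.

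On harm, the contrary evidence is disclosed in Section 1.2, from a different procedure, and Section 4.7 F itself frames the effect in IUD insertion as the question under study.

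**Conclusion.** No change to the plan follows. The 90% power and 48 per arm are correct, to rounding, for the 2-point difference they are stated for (90.4% or 89.8%, depending on the method). The 25% in Section 4.7 F is an undefined expectation in a benefits paragraph and is not an input to the design. Power for it could be 52% at an assumed control mean of 5, 90% at 8, or 98% if it refers to the full scale; with SD 3, these differ only through assumptions that the documents do not supply. Leaving the confidence interval out of Section 6.1 is a gap that analysts fill as a matter of routine.

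The no-harm wording in Section 4.7 A is a real inconsistency with Section 1.2, and Sections 4.7 E and F share its one-sidedness. It is a slip of wording, worth tidying if the text is ever revised, but it alters no endpoint, sample size, analysis or result. The two-sided test already allows for music increasing pain.
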